Official Title: Retrieval-Based Word Learning in Developmental Language Disorder

Grant #: R01DC014708

NCT#: NCT05325333

Date: March 1, 2022

Definition: Type of uploaded study document. Select one.

- Study Protocol: The written description of the clinical study, including objective(s), design, and methods. It may also include relevant scientific background and statistical considerations (if the protocol document includes the statistical analysis plan, use "Study Protocol with SAP and/or ICF" option). Note: All amendments approved by a human subjects protection review board (if applicable), before the time of submission and that apply to all clinical trial Facility Locations must be included.
- Statistical Analysis Plan (SAP): The written description of the statistical considerations for analyzing the data collected in the study. Includes how data are analyzed, what specific statistical methods are used for each analysis, and how adjustments are made for testing multiple variables. If some analysis methods require critical assumptions, the written description should allow data users to understand how those assumptions were verified.

Purpose

Word learning is one of the principal weaknesses in children with developmental language disorder (DLD). Our previous work has shown that special benefits accrue when these children must frequently recall newly introduced words during the course of learning, however their absolute levels of learning are still low compared to typically developing peers. In this study, we seek to increase the children's absolute levels of learning by adjusting retrieval schedules such that they might improve the initial encoding of new word forms. We include typically developing peers as a comparison group.

Participant selection

Preschool children with DLD are recruited through local speech-language pathologists and preschool teachers. Children with typical language development are recruited through advertisements in parent newsletters, preschools, and community events.

For interested families, a phone interview is used to screen for the following eligibility requirements:

- 1) current age between 4;0 and 5;11 (years; months)
- 2) monolingual English speaker; or bilingual speaker with significant English exposure from birth.
- 3) no significant neurological condition or neurodevelopmental disorder (e.g. ASD).

Informed consent is obtained at the first session and eligibility testing is then completed. To be eligible, the child must:

- 1) pass a pure tone hearing screening in both ears at 20 dB at 500, 1000, 2000, and 4000 Hz

- 2) score above 75 on a test of non-verbal intelligence (*Kaufman Assessment Battery for Children – Second Edition*).
- 3) complete the *Structured Photographic Expressive Language Test – Preschool 2* and receive a standard score in the following range:
 - a. To be included in the DLD group, children had a standard score below 87. This cutoff score has been found to show good sensitivity and specificity (Greenslade et al., 2009).
 - b. To be included in the TD group, children had a standard score above 87.

All children also complete the Peabody Picture Vocabulary Test – Fifth Edition. Parents complete a questionnaire that includes mother's total years of education. The PPVT standard scores and years of maternal education are both used as covariates in all statistical analyses.

For eligible children, 6 sessions are scheduled to complete the study.

Word learning procedure

The principal means by which we hoped to improve encoding and, as a result, subsequent recall, is to create a more gradual spacing of retrieval trials as the learning period proceeds.

In the current study, we compare our “standard” procedure to a gradual or “expanding” retrieval schedule. In both conditions, children first hear each word and what it likes, and then are immediately asked to recall this information. After these trials, the schedule for the two conditions diverge. For subsequent recall in the “standard” condition, three other words intervene between the last time the child heard the word and the time when the child is asked to recall it. In contrast, in the “expanding” condition, the spacing between study and subsequent retrieval of the word is initially narrow -- one intervening word - and expands more gradually to three intervening words.

The words in the two learning conditions - standard retrieval and expanding retrieval - are presented sequentially in separate sets. The sets are counterbalanced in order. Each set involved two learning sessions held on consecutive days with a recall test administered five minutes after the second learning session, followed by another recall test one week later. The second set begins the next week, following the same scheme as the first set.

Four novel word “forms” are learned in each set. Colored photographs appearing on a laptop screen are the visual referents for these words. We also associate each word with something the referent “likes” (although what it likes was not shown on the photograph). This serves as the “meaning” of the word. During each study trial, the novel word is mentioned three times and its meaning is mentioned once, as in: “This is a /nep/. It's a /nep/. A /nep/ likes rain”. For conditions that included retrieval trials, the child sees the picture and is asked, “What's this called? What do we call this?” and then “And what does this one like? What does it like?” Audio stimuli is pre-recorded and presented along with the visual stimuli (scanned photographs) on the laptop.

The novel words are monosyllabic (consonant-vowel-consonant) and are matched across conditions according to phonotactic probability and neighborhood density (based on Storkel & Hoover, 2010).

The two learning sessions within each set are identical. For the set constituting the standard condition, each novel word is presented initially in a study trial, followed by an immediate retrieval trial, followed by another study trial. We refer to such retrieval trials as "0" retrieval trials, reflecting the fact that there are zero words intervening between a word's study trial and its retrieval trial. After each novel word has had a 0 trial, all subsequent retrieval trials occur after three other words have intervened since the last time the word appeared in a study trial. Such trials are followed by a study trial for the same word. We refer to these retrieval trials as "3" retrieval trials, again, reflecting the number of intervening words used. The retrieval schedule for each day for the words in the standard condition is 0-3-3-3-3. However, after the second 3 trial of the four words, we insert one study trial for each word. This study trial is intended as a "refresher" under the assumption that some words will not yet be recalled at that point. The insertion of these study trials does not change the 3 spacing between a word's retrieval trial and its previous study trial. The next day has the 0-3-3-3-3 schedule with a "refresher" study trial after the second 3 trial.

For the set constituting the expanding retrieval condition, each word first occurs in a study trial, followed by an immediate retrieval trial, and then another study trial. The next two retrieval trials occur after only one other novel word has intervened since the word's most recent study trial. These retrieval trials were followed by a study trial. We refer to these retrieval trials as "1" retrieval trials, as there is one intervening word. The two remaining retrieval trials for words in this condition are 3 retrieval trials, with each retrieval trial followed by a study trial for the same word. The schedule for each day, then, is 0-1-1-3-3. After the second 1 retrieval trial for the four words in the set, a study trial is presented for each word as a "refresher," as was done for the words in the standard condition.

With this design, the two learning conditions provide the same number of exposures to the word forms and meanings, and the same number of retrieval opportunities throughout the two-day learning period. The two conditions differ only in the retrieval schedule - 0-3-3-3-3 versus 0-1-1-3-3.

See https://pubs.asha.org/doi/full/10.1044/2024_JSLHR-23-00528 Appendix A and B for an illustration of the details of words and learning schedules.

Outcome measures

Primary outcome measures:

Form Recall and Meaning Recall test at 5 minutes. For each set, after the child has completed the learning session of the second day, a five-minute break is given. Then a recall test of each word form and meaning is administered. Two items for each word form and meaning are used, with the second item for each word presented only after all four words had been tested once. Prompts used for the recall items are identical to those used in the retrieval trials ("What's this called?"; "What does this one like?").

Form Recall and Meaning Recall at one week. The Form and Meaning recall test is re-administered one week after the first day of learning.

Form Recognition at one week. Immediately following the one-week Form and Meaning Recall test, a picture-pointing recognition test is administered. The photo of each novel

word referent is shown along with the referents of the other three referents (in an array of four photos) and the child was asked, "Show me the e.g., /nɛp/."

Secondary outcome measures:

Peabody Picture Vocabulary Test – Fifth Edition is completed. Standard scores are obtained and used as a covariate in all statistical analyses.

Parents complete a questionnaire that includes mother's total years of education. Years of maternal education is used as a covariate in all statistical analyses.

Scoring

Word Form Recall measure: Eight items were used for the word form recall test for each set. Several steps are used in the scoring of children's word productions:

- 1) Productions of real words alternatives to the novel word (e.g., "cactus") are scored as incorrect.
- 2) Productions that appear to be attempts at the novel word but are not accurate are submitted to the scoring system of Edwards et al. (2004). Each consonant is awarded one point each for correct place, manner, and voicing. For vowels, one point is given for each of length, height, and backness. An additional point is credited for correct syllable shape (CVC). Given that all novel words had the syllable shape CVC, all fully adult-like pronunciations earned 10 points. For any non-adult-like production to be scored as correct, the production is required to have a higher point total than the total that would be given if the child is instead trying to produce one of the other novel words.

Meaning Recall measure: Eight items were used for the meaning recall test.

Scoring of the children's responses on the meaning recall test as correct or incorrect is straightforward, as pronunciation, even when non-adult-like, is not a factor in distinguishing among the possible meanings (e.g., grass, butterflies, rain, sun).

Form Recognition measure: Eight items were used for the form recognition test.

The child's picture pointing response is recorded at the time of test. The score for the recognition test was the number of items in which the child pointed to the correct photograph in the four-photograph array.

Data analysis plan

The first set of analyses examined the children's longer-term recall and recognition. Specifically, children's responses on the word form recall test, the meaning recall test, and the recognition test were evaluated using a series of mixed-effects models, with and without the covariates of PPVT-5 standard score and maternal education in years. The outcome was the number of correctly recalled items in a set of 8 items (as 2 items were used for each of 4 novel words). Diagnostic group (DLD, TD) was a between-participant variable; within-participant variables were learning condition (01133, 03333), and time (5-minute, 1-week, for the word form and meaning tests only). Random slopes for learning condition and time were included in the models when they were not close to zero. As a result, the random slope for the learning condition variable was included in the word form recall and meaning recall models and the random slope for time was included in the meaning recall model.

Main effects models and full factorial models that included all possible two-way and three-way interactions were tested hierarchically.

Effect sizes are reported as partially standardized beta coefficients (b_{std}), which are comparable to a Cohen's d except they represent conditional standardized mean differences, conditioned on other variables in the model. Restricted maximum likelihood (REML) estimation was used. Bootstrapped standard errors with 1,000 replicates were used to account for non-normal error terms in the meaning recall and recognition models. Stata version 17.0 was used for mixed effects model analyses (StataCorp, 2019).

Collapsing across sets, each measure has a range of 0-8 in each of the two conditions.

We hypothesized that the use of “1” retrieval trials prior to proceeding the 3 retrieval trials would increase the children’s ability to encode the novel word forms and meanings. Accordingly, we expected that recall and recognition scores would be higher for words in the expanding 0-1-1-3-3 condition than in the standard 0-3-3-3-3 condition. This was a rather stringent test given that our previous work has shown that the standard condition was more successful than comparison conditions that did not involve spacing. Nevertheless, it was necessary to attempt to improve on the standard condition given, using this retrieval schedule, children were unable to learn more than approximately half of the words employed.

We expected that the expanding condition would lead to better results than the standard condition for both the children with DLD and the children with TD. In our earlier work, group differences were often seen favoring the TD children for the standard condition but the difference was smaller than the group differences seen for the comparison conditions. The current study involve two conditions that each involved spaced retrieval, with only the particular retrieval schedule distinguishing the two. We expected that the expanding condition would show narrower differences between the two groups of children than the standard condition.

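### Age enters no model although children span 4;0 to 5;11 and the outcome is a raw 0-8 count, and the covariate statements conflict; this mainly affects the DLD-versus-TD comparison

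*Combined protocol and SAP*

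**What the plan says.** Participant selection admits children aged 4;0 to 5;11 and assigns them to DLD or TD by a language-test standard score. On covariates, the same section states: "The PPVT standard scores and years of maternal education are both used as covariates in all statistical analyses". The secondary measures under Outcome measures repeat this for PPVT-5 ("Standard scores are obtained and used as a covariate in all statistical analyses") and for maternal education ("Years of maternal education is used as a covariate in all statistical analyses").

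The Data analysis plan instead describes mixed models run "with and without the covariates of PPVT-5 standard score and maternal education in years" and does not say how the two versions are to be used. On the response it says: "The outcome was the number of correctly recalled items in a set of 8 items". On group: "Diagnostic group (DLD, TD) was a between-participant variable". Learning condition and time are within-child factors. Effect sizes are standardised coefficients, and "they represent conditional standardized mean differences, conditioned on other variables in the model".

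Age is not listed in either version of the models. The TD children are called peers, but no age matching is described.

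**The concern.** A raw recall count is not corrected for age, and a two-year span at preschool age is wide enough that older children may well score higher. A PPVT standard score is already normed for age, so adjusting for it does not remove such an effect. Group is not randomised, and the two groups are recruited through different channels. Two things follow for the DLD-versus-TD contrast: its standard error carries whatever variation age explains, and the contrast is biased if the groups differ systematically in mean age.

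The conflict over covariates bears on the same contrast. Because the reported effects are conditional on what else is in the model, the versions with and without PPVT-5 and maternal education estimate different group gaps. A reader who is told both that every analysis is adjusted and that models are run both ways cannot tell what a reported gap means.

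**Working it through.** The documents give no sample size, effect size, mean ages or age slope, so there is no planned figure to reproduce. Everything below is illustrative.

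**Inputs.** From the documents: a 24-month age window; 2 items × 4 words = 8 points. Assumed: 20 children per group; ages uniform, so SD = 24/√12 = 6.93 months; within-group correlations with a child's mean score of 0.35 (PPVT) and 0.2 (maternal education); age uncorrelated with both; age-score correlation r from 0 to 0.5. SD means the within-group SD of a child's mean score.

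**Standard error of the group contrast.** Residual variance with PPVT and education is 1 - 0.35² - 0.2² = 0.8375. The ratio of standard errors, with age to without, is √[(1 - r²/0.8375) × (1 + 3/34)/(1 + 2/35)]; the second factor (1.0294) is the price of a third covariate with 40 children.

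| r | Ratio | Change by formula | Change by simulation (4,000 runs) |
|---|---|---|---|
| 0 | 1.015 | +1.5% | +1.4% |
| 0.2 | 0.990 | -1.0% | -0.9% |
| 0.3 | 0.959 | -4.1% | -4.1% |
| 0.5 | 0.850 | -15.0% | -15.1% |

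Break-even is at r ≈ 0.155. In simulation at r = 0 the cost is 2.1% with 15 per group and 0.9% with 30. Only relative changes are given, because the absolute standard error also depends on how far the groups differ on the covariates.

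**Bias.** For a systematic difference of g months, bias = r × g/6.93. At g = 3 this is 0.087 (r = 0.2), 0.130 (r = 0.3) and 0.217 (r = 0.5) SD. Over g = 1 to 6 and r = 0 to 0.5 it runs from 0 to 0.43 SD. If the standardiser is the SD of a single score (intraclass correlation 0.3 to 0.7), the 3-month bias for r = 0.3 to 0.5 is 0.09 to 0.19 for recall and 0.11 to 0.20 for recognition. In items, slope × gap gives 0.04 to 0.60 for 0.02 to 0.10 items per month and gaps of 2 to 6 months. As a simulated check (400 trials, 6-month gap, 0.08 items per month, true group effect -1.0), the mean estimate was -1.40 without age and -0.94 with it.

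**Within-child terms, additive covariates, complete data.** In one simulated data set (20 per group, REML, random condition slope), condition (1.15, SE 0.362) and group-by-condition (-1.40, SE 0.512) were identical without covariates, with PPVT and education, and with age added. The group coefficient was -1.50, -1.54 and +0.21.

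**When that invariance fails.**
- With 10% of test cells missing, going from no covariates to all three moved condition from 1.070 to 1.044 and group-by-condition from -1.607 to -1.616.
- With three children lacking maternal education and dropped from the adjusted model, group-by-condition moved from -1.400 to -1.547. On those 37 children it was the same with or without age, so the shift comes from the change of children.
- If age modifies the schedule effect by 0.03 items per month and the groups differ by 6 months, the expected distortion of group-by-condition is 0.03 × 6 = 0.18 items before rounding and truncation at 0 and 8. Simulated means were -0.14 and -0.12 (age slopes 0.08 and 0.04; true value 0), against 0.00 and 0.03 with an age-by-condition term. An additive age term does not remove this.

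**The case against.** The strongest reply is that the design already protects what matters. Each child receives both schedules, and the stated hypotheses concern the schedule effect and a narrower group gap under the expanding schedule; none rests on the group main effect. Both groups share one age window, and assignment uses a standard score, so group is not mechanically tied to age. The covariate statements can also be read together: every analysis has an adjusted version, and the Data analysis plan adds an unadjusted one. Most of this stands, and it is why the point is minor. It does not supply an age term, and it does not tell the reader how the two versions relate.

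Four stronger readings are tempting.
- A reader might infer that leaving out age undermines the expanding-versus-standard result. It does not, under the conditions shown above.
- A reader might infer the reverse, that only the group main effect can move. That needs complete data, additive covariates, the same children in both versions and no modification of the schedule effect by age; the documents establish none of these.
- A reader might infer that the group contrast is in fact confounded by age. No mean ages are given. With 20 per group and uniform ages, a chance gap has SD 6.93 × √(2/20) = 2.2 months; a 3-month gap is therefore possible by chance alone, but chance imbalance is imprecision, not bias.
- A reader might infer that the adjusted model should decide the group comparison. PPVT-5 measures vocabulary, which overlaps with the language deficit that defines DLD, so adjustment may remove part of the disorder's own gap. The Purpose section is concerned with absolute learning levels relative to typical peers, and the unadjusted gap speaks to that directly.

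**Conclusion.** The point holds and is minor. Age is absent from every model of a raw count over a two-year age span, and the covariate statements do not agree. The main effect is on the DLD-versus-TD comparison: at 20 per group, a standard error between 1.4% smaller and about 15% larger than it would be with age in the model (r = 0 to 0.5), and a bias of about 0.09 to 0.22 SD if there is a systematic 3-month age difference (r = 0.2 to 0.5). At r = 0.2 the gain in precision is only about 1%. These sizes rest on assumed correlations, sample size and age distribution; the true size cannot be found from the documents. The predicted group-by-condition interaction is exposed only if age modifies the schedule effect and the groups differ in age, or, to a lesser degree, if data are missing or the two versions use different children.

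**What to change.** 1. Add age in months, already collected at screening, as a fixed covariate in the covariate-adjusted models.
2. Report age by group.
3. Run a model with age-by-condition as a sensitivity analysis for the predicted group-by-condition interaction.
4. Reconcile the statements under Participant selection and Outcome measures with the Data analysis plan: say that each model is fitted both ways, on the same children. Report both group gaps with their meanings, the adjusted one being conditional on vocabulary, maternal education and age. Do not demote the unadjusted gap, and do not state that the covariate rule concerns the group main effect only.
5. The Data analysis plan is written largely in the past tense and reports which random slopes were kept. If models have already been fitted, disclose the addition of age as post hoc.

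Cost: one model degree of freedom (two in the age-by-condition sensitivity model), one refit and some rewording, with no new data. If age proves unrelated to score, the standard error of the group contrast is about 1 to 2% larger.

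### Do the two descriptions of the one-week test leave the delayed primary outcomes without a usable retention interval?

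*Combined protocol and SAP*

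**What the plan says.** The timing of the delayed test appears in two places in the combined protocol and SAP.

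- **Word learning procedure.** This section gives the overall scheme. Learning in a set takes place on two days in a row, and the testing is described as follows: "with a recall test administered five minutes after the second learning session, followed by another recall test one week later". The section then adds: "The second set begins the next week, following the same scheme as the first set".
- **Outcome measures, primary.** The early test is placed on day 2: "For each set, after the child has completed the learning session of the second day, a five-minute break is given". The delayed recall test is defined by: "The Form and Meaning recall test is re-administered one week after the first day of learning". Recognition follows it in the same visit: "Immediately following the one-week Form and Meaning Recall test, a picture-pointing recognition test is administered".

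The end of Participant selection gives the visit count: "For eligible children, 6 sessions are scheduled to complete the study". The Data analysis plan uses the time points only as labels of a two-level factor: "time (5-minute, 1-week, for the word form and meaning tests only". No section gives a visit window.

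**The concern.** Two sections appear to start the same week on different days. In the procedure section, the nearest event for the week to follow is the five-minute test on the second learning day. In the outcome definition, the week starts on the first learning day. Both describe the same primary outcomes, and recognition moves with delayed recall because it is given straight afterwards.

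If some testers worked from one section and some from the other, the retention interval would vary between children, or between a child's two sets. Variation between children would add noise to the delayed scores. Variation aligned with condition or group would bias the comparison concerned. The contrast between five minutes and one week would also span an interval that a reader cannot state exactly. The start of the second set is given only relative to the first, so one may also ask whether the first set's delayed test always comes before new learning begins.

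**Working it through.** **1. Day count.** Take the first learning session as day 1 and the second, with its five-minute test, as day 2.

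| Count starts from | Delayed test | Days since last exposure | Days since first session |
|---|---|---|---|
| Second-day test (Word learning procedure, natural reading) | 2 + 7 = day 9 | 9 − 2 = 7 | 9 − 1 = 8 |
| First learning day (Outcome measures) | 1 + 7 = day 8 | 8 − 2 = 6 | 8 − 1 = 7 |

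The gap is 1 day: 1/7 = 14% of the longer interval, or 1/6 = 17% of the shorter. These are percentages of elapsed time, not of any outcome.

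**2. Outcomes touched.** Counting measure by time point gives five primary outcomes: form and meaning recall at five minutes, form and meaning recall at one week, and recognition at one week. The last three carry the ambiguity.

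**3. Does other text settle it?** Six sessions = 2 sets × (2 learning visits + 1 delayed test), which fits either count. The analysis section's label fits either as well. So the documents do not prove which was intended.

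**4. One count used throughout.** The documents give no forgetting rate, so assume exponential loss at k = 0.02 to 0.05 per day. One extra day multiplies every mean by exp(−k), that is 0.980 to 0.951.

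- Absolute score of 4: 4 × (1 − 0.980) = 0.08 to 4 × (1 − 0.951) = 0.20 items.
- Difference of 1 item between conditions: 1 × (1 − 0.980) = 0.02 to 1 × (1 − 0.951) = 0.05 items.

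Both conditions are shifted by the same day, so the difference is slightly rescaled and keeps its direction. The same holds for the two groups if they share the rate.

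**5. The count drifting between first and second set.** Let δ be the true difference, expanding minus standard, and let d be the loss from testing the second set a day later. Children with expanding second show δ − d, and children with standard second show δ + d. With set order counterbalanced in equal halves, the average is ½(δ − d) + ½(δ + d) = δ. If the loss is proportional to the score, the two values of d differ slightly. What remains is then half the change in step 4, or 0.01 to 0.025 items for δ = 1.

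**6. Counts mixed at random across children.** A one-day shift worth d items, present in a fraction p of tests, adds variance d²p(1 − p), at most d²/4. With d = 0.08 to 0.20, the added standard deviation is at most d/2 = 0.04 to 0.10 items on a 0–8 score.

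**7. Order of the sets.** The procedure section presents the sets in sequence, ends its account of a set with the delayed test, and only then starts the second set in the following week. Suppose the second set instead began on day 8. Its two learning days would be days 8 and 9, so the first set's delayed test would share a day with second-set learning under either count. The child would then attend on 2 + 2 + 1 = 5 days. Six scheduled sessions sit more naturally with a separate delayed-test visit.

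**The case for a change.** The best case for a change is that a primary outcome should have one stated time point, and this one does not have it throughout the text. The remaining text does not resolve the difference. A team repeating the study from the procedure section would test a day later than a team working from the outcome definition. The time factor enters the models with its interactions, so the length of the interval is part of what is estimated. Correction would cost a sentence or two and no extra visits.

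The ambiguity in the nominal interval stands, as a point about reproducibility. The rest is weaker. The procedure section is an overview that names no starting day and can be read loosely as the following week. The outcome definition is explicit and sits under the outcome's own heading. The stated hypotheses concern the two schedules, and how the gap between the groups differs under them. None concerns the amount lost between five minutes and one week. Noise or bias requires testers to have followed different sections, and material bias requires that to line up with condition or group. The documents show neither. A visit window and an analysis by days since learning would answer a problem that has not been shown to exist.

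**Conclusion.** The two sections do differ, by one day: 6 against 7 days after last exposure, in three of five primary outcomes. This is a clerical inconsistency that an analyst or tester would resolve by following the explicit outcome definition. No change to the plan follows. Reconciling the wording would help a reader who wants to repeat the study, but it would alter no analysis or conclusion.

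This rests on one count being used for every child and both sets, which agrees with the instruction that the second set repeat the scheme of the first. If that failed between sets, counterbalancing would remove nearly all of the effect on the condition comparison. If it failed at random, the added spread would be at most about 0.1 items under the assumed 2–5% daily loss. The conclusion would change only with evidence that the interval differed systematically by condition or by group, and the documents contain none. The mismatch itself is certain. The item figures depend on the assumed forgetting rate and serve only to show scale.

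### Set order is counterbalanced but no model has a set-position term; with equal orders, a first-to-second-set shift overstates the schedule effect's standard error and makes its test conservative

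*Combined protocol and SAP*

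**What the plan says.** Under Word learning procedure, the words for the two schedules are "presented sequentially in separate sets". On allocation the section says only "The sets are counterbalanced in order". It gives no number of children per order and does not say whether order is balanced within the DLD and TD groups. On timing: "The second set begins the next week, following the same scheme as the first set".

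The Data analysis plan gives the model terms: "Diagnostic group (DLD, TD) was a between-participant variable; within-participant variables were learning condition (01133, 03333), and time". Time here means the 5-minute versus the 1-week test within a set, and it applies to the two recall outcomes only. The models are fitted "with and without the covariates of PPVT-5 standard score and maternal education in years", as main-effects models and then with all two- and three-way interactions of the listed factors. On random effects, "the random slope for the learning condition variable was included in the word form recall and meaning recall models"; the recognition model has no such slope. Set position, order and sequence appear in no model, and no check for an order effect is described.

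The closing paragraph of the plan states a hypothesis about the group-by-condition interaction: "We expected that the expanding condition would show narrower differences between the two groups of children than the standard condition".

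**The concern.** This is a two-period crossover in structure, analysed without a period term. By the second set a child has already been through the same procedure and prompts, so practice, familiarity or fatigue could move scores up or down. No planned term can absorb such a shift. Condition is balanced against set position, time varies within a set, and the two covariates are constant within a child.

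Counterbalancing protects the estimate but not its reported standard error. The shift pushes the expanding-minus-standard difference up in one order and down in the other, and the model reads that spread as random variation between children. In the recall models it goes into the random condition slope. In the recognition model, with one score per condition, it goes into the residual.

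The effect falls on the main schedule contrast, which the plan itself describes as demanding because the comparator already outperformed unspaced learning. An overstated standard error could let a real benefit be read as no benefit. In addition, if the orders analysed are unequal, the schedule effect is biased. If the inequality differs between DLD and TD, so is the interaction on which the plan states a hypothesis.

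**Working it through.** **Inputs from the documents.** Two sequential sets, order counterbalanced, the model terms above, and a 0–8 score per condition. The documents give no sample size, SD, significance level, expected effect or shift, so there is no stated figure to reproduce.

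**Assumed inputs.** N = 40 children in equal orders; s = 2 items, the SD of the within-child difference (expanding minus standard) apart from any shift; schedule effect τ = 0.8 items; two-sided 5% level; shift p = 0.5, 1.0 or 1.5 items. Ranges: N = 30 to 60 and s = 1.5 to 2.5.

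**Algebra.** The expected within-child difference is τ + p when the expanding schedule comes second and τ − p when it comes first.

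- Equal orders: the mean difference has expectation τ, and its true variance is s²/N.
- A model without set position estimates that variance as about (s² + p²)/N.
- Ratio of reported to correct standard error: √(1 + p²/s²).

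At s = 2 and p = 1.0 the ratio is √(1 + 1/4) = 1.118. The correct standard error is 2/√40 = 0.316, and the model reports about √5/√40 = 0.354.

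**Power and type I error.** Paired-difference simulation, N = 40, s = 2, 20,000 replicates:

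| Shift p (items) | SE ratio | Power without term | Power with term | Type I error without | Type I error with |
|---|---|---|---|---|---|
| 0.5 | 1.031 | 67.1% | 69.2% | 4.3% | 4.9% |
| 1.0 | 1.118 | 60.7% | 69.3% | 3.0% | 5.1% |
| 1.5 | 1.250 | 50.1% | 69.7% | 1.4% | 5.0% |

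With no shift, power is about 69% with or without the term. Over the N and s ranges, with the effect held at 0.8, the power loss is about 1 to 3 points at p = 0.5, 3 to 13 at p = 1.0 and 9 to 29 at p = 1.5.

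**Mixed-model checks (REML, N = 40).**

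- Recall layout, two test times and a random condition slope, 300 replicates per shift: standard error ratios of 1.034, 1.120 and 1.260 for the three shifts. The condition estimate is identical with and without the term.
- Recognition layout, random intercept only, one-item shift, 120 replicates: mean standard error 0.286 without the term and 0.239 with it, against a true SD of 0.235. Type I error is 1.7% and 5.8%.

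**Unequal orders (splits assumed for illustration).**

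- 22 versus 18 overall: bias in the schedule effect = p(22 − 18)/40 = 0.1p. With the term, 0.
- 11/9 in one group and 9/11 in the other, common shift: interaction bias = p(2/20) − p(−2/20) = 0.2p. With the term, 0.
- 11/9 in both groups, shifts differing by d: interaction bias = (2/20)d = 0.1d. A common set-position term leaves 0.1d; a group-by-set-position term removes it.

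**The case against.** The case against rests on materiality. The design already deals with order by counterbalancing, and with equal orders the point estimates, and so the numerators of the reported effect sizes, do not move. The estimator's true sampling variance is also unchanged. Only the reported standard error is wrong, in the conservative direction, so balanced orders cannot produce a false claim for the expanding schedule. Nothing in the documents reports or predicts a shift. The large losses need a shift of 1.5 items, almost twice the assumed 0.8-item effect; at 0.25 items the power loss over the same ranges is only 0.1 to 0.6 points. The unequal splits are illustrations, and at 22/18 with N = 40 and s = 2 the type I error stays below 5% (4.6%, 3.8% and 2.7% for the three shifts). Finally, the checks omit the bootstrap standard errors planned for meaning recall and recognition and the random time slope planned for meaning recall.

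Most of this is right and limits the point. The test is conservative only when orders are equal or nearly so. If order were set by a coin flip for each child, the test would be about nominal (4.8% to 5.2% at a shift of half of s) but still less precise than with the term. A fixed 60/40 split at that shift gives a bias of (0.6 − 0.4) × 0.5s = 0.1s and a type I error of about 6% to 8%. On the bootstrap, the resampling unit is not stated; resampling children without stratifying by order would carry the same extra variance, so the direction should hold although the exact figures are not shown for those models. None of this supplies the missing term or gives a reason to leave it out, since at zero shift the term costs essentially no power.

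**Conclusion.** The point holds. No planned model contains a term that can absorb a shift between the first and second set. With equal orders the consequence is an overstated standard error and a conservative test of the schedule effect, not a false-positive risk. The factor is √(1 + p²/s²): 3%, 12% and 25% for shifts of 0.5, 1.0 and 1.5 items when s = 2.

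Whether this matters in this trial cannot be settled from the documents, because sample size, SD, effect and shift are all assumed here. Bias in the schedule effect or in the group-by-condition interaction depends on unequal analysed orders, which the documents neither show nor exclude. The change should be made because it is nearly free and protects the main contrast, but the omission does not invalidate the design.

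**What to change.** - Add set position (first or second set) as a fixed effect in every form recall, meaning recall and recognition model.
- State how order is allocated within DLD and TD, and report the number of analysed children in each order by diagnostic group.
- If orders are unequal within groups, add a group-by-set-position term as a sensitivity analysis, since a common shift term does not fully protect the interaction when the groups shift by different amounts.
- If the bootstrap resamples children, say so and state whether it is stratified by order.

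The cost is one degree of freedom per model (two with the sensitivity term) and one row of counts. No new data are needed. The term handles a shift common to both orders; it does not correct carryover that depends on which schedule came first.
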